5.3 Duration of Therapy

Duration of therapy will depend on individual response, evidence of disease progression and tolerance. In the absence of treatment delays due to adverse events, treatment may continue indefinitely until one of the following criteria applies:

- Disease progression requiring an alternative therapy. Note: In some cases, despite disease progression by RECIST criteria, participants may be continued on study drug if deemed beneficial by the participant and investigators, and if approved by the Principal Investigator/Sponsor.
- Adverse event(s)
- Abnormal laboratory value(s)
- Abnormal test procedure result(s)
- Protocol violation
- Intercurrent illness that prevents further administration of treatment,
- Participant demonstrates an inability or unwillingness to comply with the regimen and/or documentation requirements
- Participant decides to withdraw from the study, or
- General or specific changes in the participant's condition render the participant unacceptable for further treatment in the opinion of the treating investigator.
- Death

All cancer medications and/or therapies given to the participant after the last dose of study treatment will be recorded.

5.4 Permitted Treatment

All routine and appropriate supportive care, including blood products, will be provided during this study, as clinically indicated, and in accordance with standard of care practices.

Palliative radiation therapy will be permitted for participants with symptomatic bone metastases or CNS metastases as long as they have demonstrated stability in terms of systemic disease. Disease stability for these purposes will be defined as complete response, partial response, stable disease or clinical benefit in the opinion of the Investigator. For participants undergoing radiation, AUY922 must be held for at least 7 days prior to initiation of radiation. AUY922 may be resumed no sooner than 72 hours after completion of radiation.

5.5 Study Drug Discontinuation

Participants who discontinue study treatment should be scheduled for an End of Treatment Visit within 7 days after discontinuing study treatment, at which time all of the assessments listed for the End of Treatment Visit will be performed. The date and reason for stopping treatment will be recorded.

CONFIDENTIAL

This document is confidential. Do not disclose or use except as authorized.

Page 22 of 69

All participants who discontinue study treatment, including those who refuse to return for the final 28-Day Follow-up Visit, should be contacted for safety evaluations, anti-neoplastic therapies received after discontinuation of study drug, and survival information ≤ 28 days following the last dose of study treatment. Participants should continue to be followed every 12 weeks for the start date of new anti-neoplastic therapies (if not obtained within 28 days of last dose) and survival information until death or one year past the last participant last visit, whichever comes first.

Participants whose treatment is interrupted or permanently discontinued due to a study-related adverse event or abnormal laboratory value must be followed at least once a week for 4 weeks and subsequently at 4 week intervals, until resolution or stabilization of the event, whichever comes first. If a participant requires a delay of ≥ 21 days since the last dose of AUY922, the participant must be discontinued from study treatment. However, the participant will continue to be followed for toxicity as previously described. In addition, attempts should be made to follow the participant every 12 weeks after discontinuation from the study until disease progression, initiation of other anticancer therapy or study termination.

Participants who discontinue study treatment for reasons other than disease progression will be restaged every 12 weeks (± 7 days) until start of another anticancer treatment. An end of study scan is required if the participant is discontinued from treatment for any reason other than disease progression and the last scan was performed ≥ 4 weeks previously.

Participants who discontinue study treatment should be contacted for survival information by telephone every 12 weeks after last participant last visit up to a year.

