5.1 Agent Administration

5.1.1 AUY922

AUY922 will be administered by a 1 hour (+10 minute window period) intravenous infusion (in 5% glucose/dextrose) at 70 mg/m² on days 1, 8, and 15 of each treatment cycle (21 days in duration). A scheduled dose may be administered \pm 48 hours of the scheduled day due to public or religious holidays. If a peripheral line is used for the infusion of the study drug, the injection site should be monitored carefully during the time of infusion.

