6.2 AUY922 Dose Modifications / Delays

Toxicity will be assessed using the NCI-CTC for Adverse Events, version 4.02 (CTCAE v4.02)

For participants who are unable to tolerate the protocol-specified dosing schedule, dose adjustments are permitted in order to keep the participant on study drug (Tables 6-1). If the participant experiences unacceptable toxicities, treatment with the study drug must be suspended until the toxicities return to \leq CTCAE grade 1. Special instructions are provided for QTcF, gastrointestinal, and ocular toxicities. The criteria for interruption and re-initiation of AUY922 treatment are outlined in Table 6-1.

CONFIDENTIAL

This document is confidential. Do not disclose or use except as authorized.

Page 24 of 69

Table 6-1 Criteria for interruption, dose reduction and re-initiation of AUY922 study treatment

Recommended dose modifications for AUY922	
Worst toxicity	During a cycle of therapy
CTCAE grade* (value)	
No toxicity	Maintain dose level
Hematologic	
Neutropenia (ANC)	
Grade 1 (ANC < LLN - 1500/mm ³)	Maintain dose level
Grade 2 (ANC < 1500 - 1000/mm ³)	Maintain dose level
Grade 3 (ANC < 1000 - 500/mm ³)	Omit dose until resolved to ≤ grade 1 If resolved in ≤ 7 days, maintain dose level If resolved in > 7 days, then dose reduce to 54 mg/m ²
Grade 4 (ANC < 500/mm ³)	Omit dose until resolved to ≤ grade 1, then dose reduce to 54 mg/m ²
Febrile neutropenia (ANC < 1.0 x 10 ⁹ /L, fever ≥ 38.5°C)	Omit dose until resolved, then dose reduce to 54 mg/m ²
Thrombocytopenia	
Grade 1 (PLT < LLN - 75,000/mm ³)	Maintain dose level
Grade 2 (PLT < 75,000 - 50,000/mm ³)	Omit dose until resolved to ≤ grade 1 If resolved in ≤ 7 days, maintain dose level If resolved in > 7 days, then dose reduce to 54 mg/m ²
Grade 3 (PLT < 50,000 - 25,000/mm ³)	Omit dose until resolved to ≤ grade 1 If resolved in ≤ 7 days, maintain dose level If resolved in > 7 days, then dose reduce to 54 mg/m ²
Grade 4 (PLT < 25,000/mm ³)	Omit dose until resolved to ≤ grade 1, then dose reduce to 54 mg/m ²
Renal	
Serum creatinine	

Recommended dose modifications for AUY922	
During a cycle of therapy	
Worst toxicity	
CTCAE grade* (value)	
Grade 1 (> ULN - 1.5 x ULN; >1 - 1.5x baseline)	Maintain dose level
Grade 2 (> 1.5 - 3.0 x ULN; >1.5 - 3.0x baseline)	Omit dose until resolved to ≤ grade 1, then dose reduce to 54 mg/m ²
Grade 3 (> 3.0 - 6.0 x ULN; >3x baseline)	Omit dose and discontinue patient from study
Grade 4 (> 6.0 x ULN)	Omit dose and discontinue patient from study

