Diarrhea	
Grade 1	Maintain dose level
Grade 2 (see Section 6.3.1 for recommended treatment algorithm)	Omit dose until resolved to grade 1 or baseline If resolved in ≤ 7 days, maintain dose level If resolved in > 7 days, dose reduce to 54 mg/m ²
Grade 3 (see Section 6.3.1 for recommended treatment algorithm)	Omit dose until resolved to grade 1 or baseline, then dose reduce to 54 mg/m ²
Grade 4 (see Section 6.3.1 for recommended treatment algorithm)	Omit dose until resolved to grade 1 or baseline, then dose reduce to 54 mg/m ² If grade 4 toxicity lasts < 24 hours, then dose reduce to 54 mg/m ² . If grade 4 toxicity recurs, discontinue treatment. In the event grade 4 toxicity lasts > 24 hours despite optimal use of anti-diarrheal, discontinue treatment.
Visual symptoms or signs	
Grade 1	Maintain dose level
Grade 2	Omit dose administration until resolved to ≤ grade 1 (or baseline), then continue treatment with AUY922 at the current dose level If visual symptoms ≥ Grade 2 recur upon re-exposure to AUY922, omit dose until resolution to ≤ Grade 1, then dose reduce to 54 mg/m ² and maintain this dose level. If visual symptoms ≥ Grade 2 recur at a dose of 54 mg/m ² , then the participant should be discontinued from the study.
Grade 3	Omit dose administration until resolved to ≤ grade 1 (or baseline), then dose reduce to 54 mg/m ²
Grade 4	Omit dose administration and discontinue patient from study
Other adverse events**	
Grade 1 or 2	Maintain dose level
Grade 3	Omit dose until resolved to ≤ grade 1, then dose reduce to 54 mg/m ²
Grade 4	Omit dose and discontinue participant from study

CONFIDENTIAL

This document is confidential. Do not disclose or use except as authorized.
Page 28 of 69

Recommended dose modifications for AUY922	
Worst toxicity	During a cycle of therapy
CTCAE grade* (value)	
All dose modifications should be based on the worst preceding toxicity.	
Each participant is allowed only one dose reduction. Participants must discontinue treatment with AUY922 if, after treatment is resumed at a lower dose, the same toxicity recurs with the same or worse severity. Similarly, participants who have already required prior dose reduction to 54 mg/m ² for a given toxicity must be discontinued from treatment with AUY922 if a separate toxicity occurs that would otherwise require dose modification.	

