If a participant requires a dose interruption of > 28 days from the last dose, then the participant must be discontinued from the study. Participants who discontinue the study for a study related adverse event or an abnormal laboratory value must be followed.	
*Common Toxicity Criteria for Adverse Events (CTCAE Version 4.0).	
**During the administration of AUY922, the infusion should be stopped if the participant experiences CTCAE grade 2 cardiovascular toxicity or any ≥ CTCAE grade 3 toxicity.	

Participants who experience adverse events that require dose reduction will be treated at 54 mg/m² upon resolution of the adverse event.

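### Section 5.5 and the Table 6-1 footer set different maximum dose gaps (≥ 21 and > 28 days from the last dose), with no rule on which prevails for days 21 to 28

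*Combined protocol and SAP*

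**What the plan says.** Section 5.5 (Study Drug Discontinuation) reads: "If a participant requires a delay of ≥ 21 days since the last dose of AUY922, the participant must be discontinued from study treatment". It then keeps the participant in follow-up for toxicity.

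The footer of Table 6-1, in Section 6.2, reads: "If a participant requires a dose interruption of > 28 days from the last dose, then the participant must be discontinued from the study".

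Section 6.2 names the table as the place to look: "The criteria for interruption and re-initiation of AUY922 treatment are outlined in Table 6-1". It does not mention Section 5.5.

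Several rows of Table 6-1 hold the drug until recovery and then restart it:

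- Grade 4 neutropenia: "Omit dose until resolved to ≤ grade 1, then dose reduce to 54" mg/m², with no time limit in the row.
- A first grade 2 visual event: hold until recovery, "then continue treatment with AUY922 at the current dose level", again with no time limit.
- Grade 3 neutropenia and grade 2 or 3 thrombocytopenia: "If resolved in > 7 days, then dose reduce to 54" mg/m².
- Grade 2 diarrhea: "If resolved in > 7 days, dose reduce to 54" mg/m².

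Dosing is weekly, "on days 1, 8, and 15 of each treatment cycle (21 days in duration"). Section 5.7 gives a general 48-hour dosing window. Section 5.1.1 ties its ± 48 hours to public or religious holidays.

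**The concern.** These are two values for one operative safety stopping rule. Both are mandatory and both run from the last dose. Where a Table 6-1 row sets no time limit of its own, the maximum gap is the only outer limit on restarting, and the protocol gives that limit twice with different numbers.

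A participant whose toxicity resolves on day 24 must be off treatment under Section 5.5. A clinician who follows Section 6.2 to Table 6-1 finds nothing there to stop a restart at 54 mg/m² or, after a first grade 2 visual event, at the current dose. At stake are consistent dosing across the participating institutions and control of re-exposure after slow recovery. Assessment changes too: under Section 5.5, a participant stopped for a reason other than progression moves from scans every 6 weeks to every 12.

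A separate minor ambiguity lies in Table 6-3. Acuity grades 1 to 3 refer to either eye, while the note beneath refers to the better eye. The note may be meant for grade 4 only, so this is not a proven conflict. It matters because an unresolved loss of two or more lines in one eye keeps the dose on hold under the first reading and may cause no hold under the second.

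**Working it through.** **The two rules.** Let d be days since the last dose, with the last dose on day 0.

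- Section 5.5 bars re-dosing if d ≥ 21.
- The Table 6-1 footer bars it if d > 28.
- Up to day 20 neither bars it. From day 29 both do. On days 21, 22, 23, 24, 25, 26, 27 and 28 only Section 5.5 does: 28 − 21 + 1 = 8 days.

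**On the weekly schedule.** After k consecutive omitted doses, the next nominal dose falls on day 7(k + 1). The last column applies the 48-hour window as ± 2 days. It is illustrative, because Section 5.1.1 allows that shift for holidays and its use after a toxicity hold is not settled.

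| Doses omitted | Nominal day | Nominal day: 5.5 / Table 6-1 | With ± 2 days |
|---|---|---|---|
| 1 | 14 | allowed / allowed | 12–16: both allow |
| 2 | 21 | barred / not barred | 19–20: both allow; 21–23: only 5.5 bars |
| 3 | 28 | barred / not barred | 26–28: only 5.5 bars; 29–30: both bar |
| 4 | 35 | barred / barred | 33–37: both bar |

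**By day of resolution** (onset day + duration).

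- Up to day 14: no conflict. Grade 2 diarrhea starting on day 2 and lasting 9 days resolves on day 2 + 9 = 11 and is re-dosed on day 14 under either rule.
- Days 15 to 20: a conflict only if the dose waits for nominal day 21. Whether it must wait depends on the window.
- Days 21 to 28: a conflict with or without the window, because re-dosing cannot come before day 21. Grade 2 diarrhea starting on day 7 and lasting 15 days resolves on day 7 + 15 = 22.
- After day 28: stopped under both rules.

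**A second route into the disputed days.** Section 5.4 holds the drug for at least 7 days before palliative radiation and at least 72 hours (3 days) after it. The minimum gap is 7 + s + 3, where s is the number of days from first to last fraction. A course with s = 11 to 18 gives 21 to 28 days. Course length is an assumption; the documents give none.

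**How often.** The documents give no rate for gaps of 21 to 28 days. For an assumed per-participant chance p, the expected number is 20p and the chance of at least one is 1 − (1 − p)^20:

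| Assumed p | Expected of 20 | At least one |
|---|---|---|
| 1% | 0.2 | 18% |
| 5% | 1.0 | 64% |
| 10% | 2.0 | 88% |

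These figures show a range. They are not evidence that such gaps are common.

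**The stated design.** The rule of at least 4 responses in 20 has exact power 0.893 at a 30% response rate (stated 89%) and type 1 error 0.133 at 10% (stated 13%). Neither calculation uses the gap limit.

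**The case against.** A compliant path exists. Section 5.5 is unconditional, and the footer never authorises re-dosing on days 21 to 28; it only adds a later stop. A site that follows Section 5.5 breaks neither rule. That stands, and it limits the seriousness. But Section 6.2 sends the restart decision to the table, where nothing warns of a stricter limit elsewhere.

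The stated consequences also differ: off study treatment in Section 5.5, off the study in the footer. One could read these as two tiers. The table's own usage argues against that: it covers interruption and re-initiation of treatment, and its rows use removal from study as the dosing action. Even read literally, the footer leaves days 21 to 28 open.

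The practical effect is likely to be small. Section 6.3.3 reports that earlier visual symptoms typically resolved within one to two weeks after a dose, and Section 2.3.3.2 reports that every grade 3/4 adverse event was below 10%. Fifteen days of grade 2 diarrhea would be atypical, since Section 6.3.1 escalates to hospital care when loperamide and opiates fail. All of this is fair, although neither reported figure measures gap length and the grade 3/4 rate does not cover the grade 2 holds. In the same earlier study, any-grade diarrhea was 73% and visual events 71%, and Table 6-1 holds the dose for both from grade 2.

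**Conclusion.** The inconsistency is real: two mandatory limits, counted from the same point, disagree on 8 days, and no text reconciles them. The disputed nominal doses are those on days 21 and 28. This conclusion needs no assumption about the dosing window or about frequency. How many participants would be affected is unknown and probably few.

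The effect is on dosing consistency and on re-exposure after slow recovery. The number of participants, the decision rule, the power and the type 1 error do not change. The point should be fixed because it concerns a safety stopping rule and the remedy is cheap. The Table 6-3 ambiguity is minor and separate, and the conclusion does not depend on it.

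**What to change.** State one limit, counted from the last dose, in both Section 5.5 and the Table 6-1 footer. The default should be ≥ 21 days, the stricter of the two. If the sponsor intends restarts after slow recovery to remain possible up to day 28, use > 28 days in both places. Give the same consequence in both: off study treatment, with follow-up continuing.

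In Table 6-3, keep either eye (the worse-affected eye) for grades 1 to 3, and limit the better-eye note expressly to grade 4 or delete it.

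The cost is amendment wording only, with no change to sample size, decision rule or analysis. Choosing ≥ 21 days ends treatment for participants whose toxicity resolves on days 21 to 28. Choosing > 28 days permits their re-exposure.

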5. TREATMENT PLAN

Treatment phase:

Participant's screening evaluations will commence after the patient signs informed consent and will be concluded within 21 days prior to the first day of dosing.

All participants will receive AUY922 intravenously at 70 mg/m² weekly in a 21 day cycle. Treatment duration will continue until disease progression (defined by RECIST), unacceptable toxicity, participant withdrawal, death or discontinuation from the study for any other reason.

Efficacy will be evaluated by radiological assessments using RECIST version 1.1 criteria at baseline and after every two cycles.

Follow-up visits:

Participants who discontinue treatment should have a follow-up visit 28 (± 7) days after the end of treatment visit to follow-up for adverse events (AEs) and serious adverse events (SAEs) that may occur after discontinuation.

Follow-up period:

Any participant who discontinued study treatment for any reason other than disease progression, death or withdrawal of consent will continue to have tumor assessments every 12 weeks (± 7 days) until the participant starts another anti-cancer therapy. This includes surgical procedures for palliative treatment.

All participants will be followed for PFS and OS for a duration of up to a year after the last participant's last visit.

CONFIDENTIAL

This document is confidential. Do not disclose or use except as authorized.

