5.6 Follow-up Assessments and Study Completion

After discontinuation of study drug treatment, participants will continue to be evaluated for safety and survival data. The following visits will be performed:

28 Day Safety Visit: All participants will have a follow-up visit scheduled 28 days (± 7 days) after the last dose of study treatment to follow-up for AEs and SAEs. AEs and SAEs that are still ongoing at the time of discontinuation and considered as related to study treatment will continue to be followed weekly until resolution, stabilization of condition, or end of study.

Treatment Follow-up Period: Any participant who is discontinued from study treatment for any reason other than disease progression will continue to have tumor assessments every 12 weeks until progression, death or until a new anti-neoplastic therapy is initiated. The investigator, or his/her designee, will continue to collect information until the first initiation of additional anti-neoplastic therapies for each discontinued participant until one year following last participant last visit.

All participants who have progressed during study treatment or during the Treatment Follow-up Period will be followed every 12 weeks for survival up to 1 year after the last participant is discontinued from the study.

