	-21 to -1	1	2	3	8	15	1	8	15	15	28 days of last dose (± 7 days)	

4. ECG – At end of treatment, ECGs can be obtained at any time.
 
5. A serum pregnancy test must be obtained prior (within 72 hours) to the first administration of AUY922. The test should be repeated prior to D1 of every subsequent odd numbered cycle (within 72 hours) or if pregnancy is suspected.
 
6. Standard ophthalmologic assessments will be required at baseline and follow-up exams will be conducted at the time when visual symptoms are reported (if any), at cycle 3 day 1 (± 2 days) if no visual symptoms are reported, and at study discontinuation (± 7 days).
 
7. A CT scan with contrast of the chest, abdomen, and pelvis will be performed on participants at baseline (screening) -21 to -1 days prior to study drug administration. The same type of imaging modality (CT with contrast or MRI) used at screening must be used for all subsequent follow-up assessments. Follow-up CT/MRI scans will be performed every 6 weeks (± 7 days) from start of study treatment.
 
8. In the event that a participant is discontinued from treatment for any reason other than disease progression, an end of treatment CT/MRI is recommended to be performed if the last scan was conducted ≥ 4 weeks previously. Such participants who discontinue study treatment for reasons other than disease progression will be re-staged every 12 weeks (± 7 days) until start of another anti-cancer treatment. A partial or complete response warrants confirmation assessment no sooner than 4 weeks and no later than 6 weeks after its initial observation. An end of study scan is required if the participant is discontinued from treatment for any reason other than disease progression and the last scan was performed ≥ 4 weeks.
 
9. In consented participants, an optional biopsy will be performed at baseline and again at the end of treatment.
 
10. Participants will be followed for survival every 12 weeks after discontinuing the trial. Follow-ups may be conducted over the telephone.
												

CONFIDENTIAL

This document is confidential. Do not disclose or use except as authorized.

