13.3 Analysis of Secondary Endpoints

Secondary endpoints will be analyzed for exploratory purposes only. Participants with ALK TKI resistance and those with ALK TKI intolerance will be analyzed collectively and as distinct cohorts for all endpoints.

Disease Control Rates: Disease control rates (DCR) will be scored according to RECIST version 1.1 criteria and consist of complete response, partial response, and stable disease.

Progression-free and Overall Survival Rates: Progression-free survival (PFS) will be defined as the time from the date of study enrollment to the date of first documented progression or death due to any cause. Overall survival will be defined as the time from study enrollment to death from any cause.

Safety: Toxicity will be assessed using CTC v4.02 criteria. All participants who receive any amount of study drug will be evaluable for toxicity.

KRAS Mutations: Concurrent KRAS mutations will be reported as frequencies. Descriptions of the specific KRAS mutations will also be reported.

ALK Translocation Variant: Exploratory, hypothesis-generating analysis will be performed to correlate different ALK translocation variants with response to treatment with AUY922.

Mechanisms of Resistance: Exploratory, hypothesis-generating analyses will be performed to correlate any findings from the various potential biomarker studies listed in Section 8 with the primary and secondary study endpoints above.

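### Scans go from 6-weekly on AUY922 to 12-weekly after stopping without progression, so PFS dated at first documented progression is overstated on average, by a small amount

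*Combined protocol and SAP*

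**What the plan says.** Table 8-1, footnote 7, sets the on-treatment schedule: "Follow-up CT/MRI scans will be performed every 6 weeks (± 7 days) from start of study treatment". Sections 1.1, 9 and 13.1 give the same 6-week interval.

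After a stop for any reason other than progression the interval doubles. Section 5 says such participants "will continue to have tumor assessments every 12 weeks (± 7 days) until the participant starts another anti-cancer therapy". Section 5.5 has the same rule for those who "discontinue study treatment for reasons other than disease progression will be restaged every 12 weeks". Section 5.6 says they "will continue to have tumor assessments every 12 weeks until progression, death or until a new anti-neoplastic therapy is initiated". Table 8-1, footnote 8, and section 8.1.9 repeat the 12-week interval.

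Section 13.3 runs PFS from enrollment to "the date of first documented progression or death due to any cause". Sections 1.3.1 and 9.1.6 are similar. None of them gives a censoring rule, an interval-censored method or a sensitivity analysis.

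Section 13.3 calls all secondary endpoints exploratory and adds: "Participants with ALK TKI resistance and those with ALK TKI intolerance will be analyzed collectively and as distinct cohorts for all endpoints". It specifies no contrast or test between the two cohorts.

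Two provisions soften the effect. Section 5.5 makes a scan at discontinuation mandatory when the previous one is at least 4 weeks old; its sentence begins: "An end of study scan is required if the participant is discontinued from treatment for any reason other than disease progression and the last scan". Section 8.1.9 allows scans when clinically indicated. However, section 8.1.9 only recommends the discontinuation scan, and footnote 8 of Table 8-1 both recommends and requires it.

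**The concern.** A progression date read from scans is the date of the first scan after the true event. If scans are twice as far apart, that date is later on average even when the disease behaves identically. Here the interval depends on something that happens after enrollment, namely stopping AUY922 without progression. Such stops are foreseeable: Table 6-1 mandates discontinuation for several toxicities and allows one dose reduction only.

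Estimating PFS is a named secondary objective in section 1.3. With a single arm there is no concurrent control in which the same artefact would occur and cancel. What is at stake is a modest, favourable error in a descriptive estimate that readers may set beside other studies.

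**Working it through.** **The plan's own figures.** The documents give no PFS figure. The quantified design statement is the response rule in section 13.1, at least 4 responders of 20. The exact binomial gives P(X ≥ 4 | n = 20, p = 0.10) = 0.133 and P(X ≥ 4 | n = 20, p = 0.30) = 0.893. These reproduce the stated 13% and 89%. No PFS date enters this rule.

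**Inputs.** From the documents: 6-week interval on treatment, 12-week interval after stopping, and a discontinuation scan if the last one is at least 4 weeks old. Assumed, because the documents are silent: the true time to progression (exponential), the share prone to stopping AUY922 for toxicity, and when they stop. The basic calculation has no deaths, new therapy or unscheduled scans.

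**Mean delay from true to recorded progression.** With hazard λ = ln 2 / median and scans every D weeks, mean delay = D / (1 − exp(−λD)) − 1/λ. For a median of 4 months (17.38 weeks), λ = 0.0399 and 1/λ = 25.07:

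- D = 6: 6 / 0.2128 − 25.07 = 3.12 weeks
- D = 12: 12 / 0.3804 − 25.07 = 6.48 weeks

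| True median (months) | Delay, 6-weekly | Delay, 12-weekly | Added (weeks) |
|---|---|---|---|
| 2 | 3.24 | 6.94 | 3.70 |
| 4 | 3.12 | 6.48 | 3.36 |
| 6 | 3.08 | 6.32 | 3.24 |
| 10 | 3.05 | 6.19 | 3.14 |

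**Effect on the whole group.** Two simulations were run, each with 400,000 participants per scenario and the discontinuation scan done.

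- *Medians 8, 13 and 26 weeks; 10% to 40% toxicity-prone; mean stopping time 9 weeks.* Between 1.1 and 6.5 of 20 participants progress while on the 12-week schedule. Their mean delay is 6.1 to 6.5 weeks against 3.0 weeks at 6-weekly scanning. Mean PFS rises by 0.2 to 1.0 week.
- *Medians 2 to 10 months; stopping uniform over 3 to 18 weeks.* At a 4-month median, mean PFS moves from 28.15 to 28.62 weeks (+0.47) if 20% stop and from 28.22 to 29.16 (+0.94) if 40% stop. Across the medians the shift is 0.37 to 0.54 week at 20% and 0.74 to 1.08 weeks at 40%.

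**Median PFS.** It was unchanged in most scenarios. At a 4-month true median with 40% stopping it went from 18 to 24 weeks, one scan interval. In simulated trials of 20, the observed median moved later in 7% to 37%.

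**Not every participant is delayed.** In the first simulation about 54% to 59% of those progressing on the 12-week schedule were recorded later and 6% to 9% earlier, because the discontinuation scan takes them off the 6-week grid. The second simulation counts everyone not yet documented as progressed at the stop. There, about 54% were later and 18% to 24% earlier.

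**Competing events.** The 12-weekly scans end at new anticancer therapy. If new therapy starts at an assumed median of 8 weeks after stopping, only about 0.2 to 1.3 of 20 have progression recorded off treatment, well below the 1.1 to 6.5 above.

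**Against sampling error.** For an uncensored exponential, the standard error of a mean of 20 is (median / ln 2) / √20, which is 2.6, 4.2 and 8.4 weeks for medians of 8, 13 and 26 weeks. A shift of 1.0 week is at most 1.0 / 2.6 = 0.38 of a standard error.

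**The case against.** The strongest reply is that this is a small effect on an exploratory endpoint. First-documented-progression dating is clearly and consistently defined, the shift is well inside sampling error with 20 participants, and section 13.3 does not name the mean as a summary. New therapy, deaths (which count as events whatever the scan schedule) and clinically indicated scans all shrink it. All of that stands. It limits the size of the point but does not remove it: the mean shift was towards longer PFS in every scenario, and a larger sample would not average it away.

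A reader might go further and infer that the resistant and intolerant cohort results are distorted relative to each other. The documents do not support that. Section 3.1 defines the cohorts by what happened on the prior ALK TKI, whereas the scan change depends on stopping AUY922, and no section links the two. With equal stopping rates and times both cohorts shift alike. A gap of about 0.9 to 1.0 week in mean PFS appears only if rates such as 50% and 10% are assumed, and nothing in the documents suggests those values. No contrast between the cohorts is planned. The intolerant group may also be tiny: if the roughly 6% crizotinib discontinuation rate in section 2.2 carried over (an assumption), 20 × 0.06 = 1.2 would be expected, with an 11.5% chance of 3 or more.

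Nor can one infer that each early stopper is recorded as progression-free for longer than an identical participant on drug. The delay holds on average only.

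**Conclusion.** The point holds as a minor one. Because the scan interval depends on treatment status and the analysis does not allow for it, exploratory PFS is overstated on average. The added delay is about 3 weeks per participant who progresses on the 12-week schedule. The rise in the group mean is about 0.2 to 1.0 week if 10% to 40% are prone to toxicity stopping.

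Both the stopping rates and the progression times are assumptions. The group figures sit at the upper end because they leave out new therapy, deaths and unscheduled scans. The median will usually stay put but can jump by about one scan interval. The primary response-rate decision is not touched. Unequal effects on the two cohorts would need different AUY922 stopping rates or times, which the documents do not show.

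**What to change.** In section 13.3, keep the PFS estimate based on the first documented date and add one sensitivity analysis beside it. Treat progression as interval-censored between the last progression-free scan and the first scan showing progression, enter deaths at their exact dates, and estimate the curve with a method for such data (for example Turnbull's). Do this for all participants pooled, and by cohort only if numbers allow.

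The cost is SAP wording and one extra analysis on scan dates already collected. The estimate will be slightly less precise and PFS slightly shorter. No scan, treatment or primary-analysis change is needed.

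Separately, reconcile section 5.5, Table 8-1 footnote 8 and section 8.1.9 on whether the scan at discontinuation is mandatory or only advised, since that scan supplies one of the interval bounds.
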